- ii) It is at the end stage of important functional organ diseases, such as malignant tumors, cardiac failure, etc.
- iii) Limb dysfunction.
- iv) Diagnosed with dementia.

Withdrawal criteria:

- i) Withdrawal of consent by the participant.
- ii) Non-compliance with study requirements (e.g., missing >25% sessions).
- iii) Significant health deterioration affecting participation.

5) Study groups

Experimental group: Older adults with MCI from Jinzhou Rehabilitation Hospital (JRH), with psychomotor rehabilitation nursing plan.

Control group: Older adults with MCI from Jinzhou Pension Comprehensive Service Center (JPCSC), without psychomotor rehabilitation nursing plan.

6) Operational definition:

- i) Mild cognitive impairment (MCI): Mild Cognitive Impairment (MCI) is defined as a condition characterized by noticeable cognitive decline beyond what is expected for an individual's age and education level, but not severe enough to interfere significantly with daily life or independent functioning. It serves as an intermediate stage between normal aging and dementia. (Petersen, R.C., 2004; B. Winblad, 2004).
- ii) Psychomotor therapy (PMT): Psychomotor therapy is a form of therapeutic intervention that focuses on the connection between psychological and motor (physical) functions (Duan Zhouying, Chen Wenhua, 2021).

7) Sample size determination

Objective No. 1 and 2: To develop and validate the psychomotor rehabilitation nursing plan through content/face validation using the Delphi method for older adults with mild cognitive impairment in promoting cognitive function.

A sample size of 8 to 15 respondents has been recommended for Delphi studies, given that smaller samples reduce reliability and bigger ones do not appear to add much value (Kenney et al., 2010). For this study, we aimed to recruit 10-12 participants.

Objective No. 3: To determine the effectiveness of the psychomotor rehabilitation nursing plan in enhancing cognitive function among older adults with mild cognitive impairment .

The sample size was calculated for specific objective 2. It was estimated by using the sample size formula compared with the average of two samples (Ni Ping et al., 2010) . The sample size calculation formula and parameters were as below:

$$N1 = N2 = 2[(t_{\alpha/2} + t_{\beta})S/\delta]^2$$

N1 is the sample content of the experimental group.

N2 is the sample content of the control group.

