Week 0-6 Tuesday Thursday 9:00-10:00 am	Psychomotor function Phase 1	
1.Do relaxation and breathing exercises before and after exercise (10 minutes).
 
2.Blink alternately, bulge left and right cheeks, and improve facial motor function (10 minutes).
 
3.(10 minutes)
  
4.(10 minutes)
  
5.Carry out upper limb gymnastics exercises to improve limb motor function (20 minutes).
	Assessment time is at the baseline (before intervention).
Week 7-12 Tuesday Thursday 9:00-10:00 am	Psychomotor function Phase 2	
1. Do relaxation and breathing exercises before and after exercise (10 minutes).
 
2.(10 minutes)
  
3.(10 minutes)
	Assessment time is at the 12 week (after intervention).

		 
1. (10 minutes)
  
2. Carry out upper limb gymnastics exercises with music to improve limb motor function (20 minutes).
	
--	--	--	--

10) Data collection and Research tool

Phase 1: To develop and validate the psychomotor rehabilitation nursing plan through content/face validation using the Delphi Method for older adults with mild cognitive impairment.

The draft of the PMT rehabilitation nursing plan will be summarized through a literature review. An expert letter questionnaire will be formulated to make the PMT rehabilitation nursing plan more suitable for MCI older adults in China, and specialist consultation will be conducted face-to-face or by email, according to the actual situation. The Delphi method was used to reach a consensus on each program's characteristics, structure, and cognitive training tasks of the PMT rehabilitation nursing plan. A panel of experts was invited to participate in the content validation by answering two rounds of questions (scale and free-text boxes) regarding the program. Changes were made between the rounds according to the results of the first round. The consensus was defined as at least 70% of the experts agreeing on the validity of a characteristic. Experts will be invited to rate the importance and feasibility of the questionnaire items. The experts will be required to provide feedback to us within 2 weeks after receiving the questionnaire. After the first round of expert inquiry, the PMT

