rehabilitation nursing program will be modified, deleted and supplemented based on the experts' scores and opinions on the items, so as to determine the second round of expert inquiry questionnaires and conduct the second round of expert inquiry. There will be a 3-week interval between the first and second rounds. After receiving the questionnaires from the experts, the inquiry results will be summarized and statistically analyzed until the experts' opinions reach a consensus, and the entire inquiry process will be terminated.

The duration of participant involvement in the Delphi method will be approximately 6 – 10 weeks in total, depending on the number of rounds required to reach expert consensus. Each Delphi round will require participants to complete the questionnaire, which is estimated to take 20 – 30 minutes per round. Between rounds, there will be a 1 – 2-week interval for data analysis and feedback preparation. While we anticipate achieving consensus within two rounds, a third or fourth round may be necessary if the responses require further refinement. In such a case, participants will be informed in advance, and their continued involvement will be requested. We will strive to minimize the burden on participants while ensuring robust and reliable results.

Phase 2: To evaluate the effectiveness of the psychomotor rehabilitation nursing plan among older adults with mild cognitive impairment.

The data will be collected from January 2025 to December 2025 in China's older adults care institutions. The data collection form was created by the researcher to record general information about older adults, such as age, gender, education level, family history of dementia, marital status, personal annual income, chronic disease. It will take no more than 5 minutes. Then, It will conduct questionnaire surveys before the intervention (baseline) and after the intervention (12 weeks). The questionnaires involved include MoCA, which has 11 questions and takes about 10 minutes; PANSS, which has 30 questions and takes about 20 minutes; HAMA-14, which has 14 questions and takes about 10 minutes; HAMD-17, which has 17 questions and takes about 15 minutes. All questionnaires will take no more than 60 minutes. Due to ethical issues, the names of the elderly participating in this study are only used for data collection, and their identity information will not be disclosed.

Data/Specimen handling:

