Quantitative analyses will be conducted using SPSS version 28. The mean, standard deviation, coefficient of variation (CV), and full score ratio of all items will be calculated. The positive coefficient and authority coefficient (Cr) of the experts will be calculated. The

authority coefficient will equal to the mean value of the expert's self-assessed familiarity and the basis of expert judgment. The coordination degree of expert opinions will be expressed by Kendall's coordination coefficient (W). The P value < 0.05 will be considered to indicate statistical significance.

Expected result (Dummy Table): The Delphi-method of the PMT rehabilitation nursing plan

Table General information of experts

Items	Groups	Number of people	Composition ratio (%)
Gender	Male		
	Female		
Age (years)	30-40		
	40-50		
	> 50		
Education level	Undergraduate		
	Master		
Years of working experience	< 10		
	10-20		
	> 20		
Professional title	Intermediate		
	Senior		
Professional composition	Nursing		
	Neurology		
	Rehabilitation Medicine		
Province	Liaoning		
	Beijing		
	Shanghai		
	Guangzhou		

Table Specific data statistical results of each item in the first round of correspondence consultation

Item	Statements	Score (±)	CV	Consensus, n (%)
1. General Aspects of The PMT Rehabilitation Nursing Plan				
1.1 The Plan Structure	Older adults will be engaged in a 12-week PMT rehabilitation nursing plan involving 2 phases (twice a week every Tuesday and Thursday 9-10 am).			
1.2 Performance Sequence	All older adults will perform the same execution/performance sequence. The tasks must take place sequentially according to the pre-defined logic. In total, the plan comprises 5 distinct tasks in each phase.			

2. Description of The PMT Rehabilitation Nursing Plan				
2.1 Phase 1 -Task 1	Do relaxation and breathing exercises before and after exercise (10 minutes).			
2.2 Phase 1 -Task 2	Blink alternately, bulge left and right cheeks, and improve facial motor function (10 minutes).			
2.3 Phase 1 -Task 3	Hand-eye coordination training: The older adults followed instructions to grab the colorful beads with their hands and slide them along the curved track (10 minutes).			
2.4 Phase 1 -Task 4	Cognitive training puzzle board: The older adults put puzzle pieces of different colors and shapes into the corresponding grooves according to the instructions (10 minutes).			
2.5 Phase 1 -Task 5	Carry out upper limb gymnastics exercises to improve limb motor function (20 minutes).			

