2.6 Phase 2 -Task 1	Do relaxation and breathing exercises before and after exercise (10 minutes).			
2.7 Phase 2 -Task 2	Hand muscle training/flexibility training/hand-eye coordination/improved circulation: The older adults held and rotated two balls with one hand according to instructions (10 minutes).			
2.8 Phase 2 -Task 3	Hand fine training/flexibility training/hand-eye coordination/endurance and concentration training (10 minutes).			
2.9 Phase 2 -Task 4	Hand-eye coordination training/cognitive ability training/fine skills training/teamwork and social interaction training (10 minutes).			
2.10 Phase 2 -Task 5	Carry out upper limb gymnastics exercises with music to improve limb motor function (20 minutes).			

Objective No. 3: To evaluate the effectiveness of psychomotor rehabilitation nursing plan in enhancing cognitive function among older adults with mild cognitive impairment.

Data entry and analysis will be performed using SPSS 28.0 software. Descriptive statistics will be used to summarize the general information of older adults. Numerical data will be presented as mean (SD) or median (IQR) based on their normality distribution. Categorical data will be presented as frequency (%). The comparison of scores of various scales are based on paired t-test statistical methods. The P value <0.05 will be considered to indicate statistically significant with 95% confidence interval (CI).

Expected result (Dummy Table): The effect assessment of the PMT rehabilitation nursing plan

Table Comparison of cognitive status between two groups ($\bar{x} \pm s$, scores)

Assessment	Before (n = 76)	After (n = 76)	Diff (95% CI)	t	P
Orientation					
Registration					
Attention and Calculation					
Recall					
Language and Praxis					
MoCA total score					

[figure not shown]
Table Comparison of psychological status between two groups ($\bar{x} \pm s$, scores)

Assessment	Before (n = 76)	After (n = 76)	Diff (95% CI)	t	P
Positive scale					
General psychopathology scale					
Negative scale					

Table Comparison of mental rehabilitation status between two groups ($\bar{x} \pm s$, scores)

Assessment	Before (n = 76)	After (n = 76)	Diff (95% CI)	t	P
Mood-related signs					
Behavioral disturbance					
Cyclic functions					
Ideational disturbance					

Study flowchart

Gantt chart & milestone

Research Activities	2024				2025				2026			
	Jan-Mar	Apr-Jun	Jul-Sep	Oct-Dec	Jan-Mar	Apr-Jun	Jul-Sep	Oct-Dec	Jan-Mar	Apr-Jun	Jul-Sep	Oct-Dec
Preliminary discussion												

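### Delphi item 1.1 rates five schedule elements as one statement, so its 70% consensus figure cannot be attributed to any one of them

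*Combined protocol and SAP*

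**What the plan says.** Section 10) Data collection and Research tool, Phase 1, sets the rule: "The consensus was defined as at least 70% of the experts agreeing on the validity of a characteristic". Experts take part by "answering two rounds of questions (scale and free-text boxes) regarding the program", and the same section states "Experts will be invited to rate the importance and feasibility of the questionnaire items". After round 1 the programme "will be modified, deleted and supplemented based on the" experts' scores and opinions.

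Section 11) Data analysis, Objective No. 1 and 2, gives a dummy table titled "Specific data statistical results of each item in the first round of correspondence consultation". Each row has one score, one coefficient of variation and one consensus n (%). Item 1.1, The Plan Structure, is a single row: "Older adults will be engaged in a 12-week PMT rehabilitation nursing plan involving 2 phases (twice a week every Tuesday and Thursday 9-10 am". Item 1.2 covers task sequence and the number of tasks per phase. Items 2.1 to 2.10 each name a task with its minutes.

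On panel size, section 7) Sample size determination says: "For this study, we aimed to recruit 10-12 participants".

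**The concern.** The rule works on a characteristic, while the row it is applied to holds five: 12 weeks, two phases, twice weekly, Tuesday and Thursday, and the 9-10 am slot. An expert who accepts the duration but doubts the frequency has one score for both. No other row rates duration, frequency, weekdays or hour. The changeover between Week 0-6 and Week 7-12 in the intervention table is not rated anywhere.

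What is at stake is what Objectives 1 and 2 can claim. The schedule could be reported as content-validated with no element of it having its own consensus figure. A failed item 1.1 would not show by its numbers which element to revise before round 2.

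**Working it through.** **Plan's own figure.** The 70% threshold is a definition, so there is no derived value to reproduce. For the stated panel sizes it requires ceil(0.70 × n) experts: 7 of 10, 8 of 11 (0.70 × 11 = 7.7) and 9 of 12 (0.70 × 12 = 8.4). Up to three dissenters are allowed at each size.

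**What agreeing means.** Experts rate both importance and feasibility, but the dummy table has one score column. The plan does not say how a rating becomes agreement, or how partial agreement with a multi-part statement is counted. Two readings are possible and must be kept apart.

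*Reading A: an expert agrees only when accepting all five elements.* With support p for each element, and assuming independent acceptance, support for the statement is p^5. The chance of consensus is P(X ≥ r), where X ~ Binomial(n, support) and r is 7, 8 or 9. The values of p are assumptions; the document gives none.

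| Support per element | Support for item 1.1 | Chance item 1.1 passes, n = 10 / 11 / 12 | Chance one element rated alone passes, n = 10 / 11 / 12 |
|---|---|---|---|
| 80% | 0.80^5 = 0.328 | 0.018 / 0.008 / 0.003 | 0.879 / 0.839 / 0.795 |
| 90% | 0.90^5 = 0.590 | 0.359 / 0.274 / 0.206 | 0.987 / 0.981 / 0.974 |
| 95% | 0.95^5 = 0.774 | 0.829 / 0.776 / 0.721 | 0.999 / 0.998 / 0.998 |

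Independence is not the only possibility. If the same experts dissent on every element, support for the statement equals support for each element and nothing is lost. At the other extreme, suppose each element sits exactly at the threshold with three dissenters, spread over as many different experts as possible. Agreement with the statement can then be max(0, n − 5 × 3) = 0 at every planned panel size.

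Under Reading A a pass is informative: everyone who agreed accepted every element, so each has at least 70% support. The harm is confined to false failures and to not knowing what caused them.

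*Reading B: an expert scores an overall impression.* The p^5 calculation does not apply. The harm runs the other way: the statement can pass while one element has less than 70% support, and the reported figure would not show it.

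The two harms cannot occur together. The plan does not say which reading holds, so neither is excluded.

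**The case against.** The strongest defence is that the numbers are not the only route to revision. Experts have free-text boxes and may be consulted face to face. Revision draws on their opinions as well as their scores, and a third or fourth round is allowed. An objection to one element can therefore be written down and acted on. This stands. A reader might infer that the Delphi cannot correct a single element; the document does not support that. Only the consensus statistic lacks the resolution, and no rule says how written dissent on one element is counted.

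Other stronger readings also fail:

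- **That the whole dose sits in one item.** Task minutes are rated in items 2.1 to 2.10 and sum to 10 + 10 + 10 + 10 + 20 = 60 per phase, matching the one-hour slot.
- **That the Delphi is the only source of the dose.** The section on the PMT rehabilitation nursing intervention plan takes the 12 weeks from the literature table, and the Delphi reviews a draft built from literature.
- **That items 2.8 and 2.9 leave experts uninformed.** Item 2.8 reads "Hand fine training/flexibility training/hand-eye coordination/endurance and concentration training (10 minutes" and names goals rather than an action. The matching cells of the intervention table appear to have held pictures that were not extracted, and section 10) lists the devices. This may be an extraction gap, and it is a separate matter.

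Two further limits are fair. The questionnaire itself is not in the document, so the item wording is inferred from a dummy results table. And Phase 2 tests the plan as one package, so no sample size or Phase 2 analysis depends on separate consensus for each element.

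**Conclusion.** The point holds in a limited form. In the only item list available, the consensus figure for item 1.1 cannot be assigned to duration, phases, frequency, weekdays or hour, although the rule is written per characteristic and agreement with a compound statement is undefined. It rests on the actual questionnaire following the dummy table.

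The size depends on the undefined reading. Under all-or-nothing agreement with independent acceptance, 90% support per element leaves about 59% for the item, with a 0.21 to 0.36 chance of consensus across 12 to 10 experts. That loss shrinks to none as dissent overlaps. Under overall impression there is no figure to give, only the possibility of an undetected weak element. This is a cheap improvement to what Objectives 1 and 2 can conclude; it does not threaten the Phase 2 comparison.

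**What to change.** Split item 1.1 into five separately rated items: total duration; number of phases and the point of changeover; sessions per week; session length; and day and time slot. Apply the 70% rule to each and give each its own row in the consensus table. If round 1 has already been run, round 2 can carry the split.

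If the item is kept whole, the minimum is to state what counts as agreeing with a multi-part item, how the importance and feasibility ratings feed into that, and how written dissent on one element is handled. Rating activity and minutes separately in items 2.1 to 2.10 is optional.

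The cost is 5 − 1 = 4 more ratings on a form estimated at 20-30 minutes, for 10-12 experts. Phase 2 recruitment is unchanged. No dose or schedule is proposed here.

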1) Research design: Quasi-Experimental Design (Non-randomized controlled trial) with experiment and control groups for comparison. Because of ethical considerations on older adults for logistical and economical wise, easy to travel, practical, less budget. Similar studies involving rehabilitation or behavioural interventions in real-world settings have widely used quasi-experimental designs. Studies by MA Handley(2018) and AD Harris (2006) demonstrated reliable outcomes using this approach.

2) Study area: Liaoning Province, China.

3) Study population

i) Reference population: Older adults living in Liaoning.

ii) Source population / sampling pool: Elderly care institutions and rehabilitation centers, Liaoning Province.

iii) Target population: Jinzhou Comprehensive Elderly Care Institution and Rehabilitation Center, Liaoning Province.

iv) Sampling frame: List of members from the two elderly care institution and rehabilitation center; Jinzhou Pension Comprehensive Service Center (JPCSC)), and Jinzhou Rehabilitation Hospital (JRH), Liaoning Province.

4) Subject criteria

Objective No. 1 and 2: To develop and validate the psychomotor rehabilitation nursing plan through content/face validation using the Delphi method.

Inclusion criteria:

- i) Professionals with ≥ 5 years of experience in geriatric care, neurological rehabilitation, cognitive rehabilitation, or psychomotor therapy.
- ii) Academic researchers with publications in related fields.
- iii) Intermediate professional title or above.
- iv) Willingness to participate in multiple Delphi rounds and provide informed feedback.

Exclusion criteria:

- i) Experts without sufficient relevant experience.
- ii) Those unable to commit to the Delphi process.

Objective No. 3: To evaluate the effectiveness of the psychomotor rehabilitation nursing plan in enhancing cognitive function among older adults with mild cognitive impairment. (Experimental and control group)

Inclusion criteria:

- i) Older adults are aged 50 years and above.
- ii) Subjective cognitive complaints from the individual or caregiver.
- iii) Screening for MCI using the Mini-Cog scores between 0-2 (SN Abayomi, 2024).
- iv) Basic language communication, listening, speaking, and understanding skills.

- v) Ability to provide informed consent.

Exclusion criteria:

- i) Diagnosed with severe psychiatric conditions (e.g., schizophrenia, major depressive disorder).

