S is the estimated value of the standard deviation between the two populations.

δ is the difference between the two averages.

The S and δ were the values of the MMSE scale decided by the researcher based on expert opinion (Liang Jingzhao, Zhi Yanmin, 2022), S= 2.75 , δ = 2.14. The level of significance (α) was 0.05, $t_{0.05/2}= 1.96$, β was 0.10, $t_{0.1}= 1.28$. By substituting the formula, 34 samples were required for each of the two groups.

An estimated 10% was added to the calculated sample size in anticipation of some missing data. The calculated sample size for this study was 76 patients (EG: 38 patients, CG: 38 patients).

8) Sampling method: Purposive sampling

9) Subject setting and participant

PHASE 1 (Delphi-method study for screening and recruitment)

The psychomotor rehabilitation nursing plan design will use Delphi-method which is an integration involving multiple expertise for the PMT development. The participants are the professionals with academic and/or practical experience in Neurology and cognitive training in China's hospitals or universities. There is no agreed method to consider someone an expert in a given field. To facilitate the selection process, it will use a simple point evaluation system. It will include all professionals with a final evaluation of at least 2 points. Regarding academic experience, it will consider the following factors: At least one publication on the

field of cognitive training (1 point) & at least one publication on the field of Neurology (1 point) OR at least one publication on the field of cognitive training in MCI (2 points). Concerning practical experience, it will consider experience in the development of a cognitive training program (1 point). Moreover, it will also consider if the professional had clinical experience in the application of cognitive training (1 point).

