Purposive sampling. Potential participants will be identified through a literature review, existing academic contacts, and a web search for cognitive training programs (for MCI or Neurology or other conditions) and the respective scientific teams. After being evaluated in accordance to the point system previously described, professionals who met the inclusion criteria (2 points or more) will be invited to participate by email. In the initial questionnaire, they will be asked to recommend other professionals who they considered to be experts in the field. Recommended professionals who met the inclusion criteria will be contacted and invited to join the expert panel.

PHASE 2 (Quasi-Experimental design for PMT rehabilitation nursing interventional study)

This experimental method will be used in Quasi-Experimental Design (Non-randomized controlled trial) with experiment and control groups for comparison. Ethics consideration on older adults which would psychologically and emotionally impact in case not selected for experimental group. This research will be carried out in Liaoning Province of China. The rehabilitation nursing intervention will be carried out for older adults with MCI admitted in two China elderly care institutions which the name is Jinzhou Pension Comprehensive Service Center (JPCSC) and Jinzhou Rehabilitation Hospital (JRH). Because of ethical consideration on older adults for logistical and economical wise, easy to travel, practical, less budget. So the experimental group is JRH, and the control group is JPCSC. Purposive sampling, whereby older adults with MCI will be selected and invited to participate the study.

The PMT rehabilitation nursing intervention plan

From Table in the literature review, we can see that most interventions lasted for 3 months. Therefore, older adults will be engaged in a 12-week PMT rehabilitation nursing plan involving 2 phases of relaxation and breathing exercises, face exercises, hand exercises and mind exercises to promote cognitive health. The experimental group will be given interventions, twice a week every Tuesday and Thursday 9-10 am along with the study

intervention. Meanwhile, the control group will be given a standard health education on cognitive health.

Table The Mind-body Exercise of Psychomotor Rehabilitation Nursing Plan

Week	Phase	Intervention methods	Assessment

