In China, various versions of the MoCA are available, including the Beijing, Changsha, and Cantonese versions, with the Beijing version being the most widely used. The cutoff scores of the MoCA Beijing version vary for different populations. According to a study by Lu et al. (2011) involving 8,411 community-dwelling older adults aged 65 years and above, the optimal cutoff scores for diagnosing MCI with the Beijing version are ≤ 13 for illiterate

individuals, ≤ 19 for those with primary education, and ≤ 24 for those with middle school education or higher. The sensitivity and specificity for identifying MCI were 80.5% and 82.5%, respectively.

ii) Psychological assessment:

The psychological of older adults was assessed by the Positive and Negative Syndrome Scale (PANSS), including the positive scale (7 items, 7~49 points), the general psychopathology scale (16 items, 16~112 points), and the negative scale (7 items, 7~49 points). The higher the score is, the worse the rehabilitation.

The reliability and validity of the Chinese version of PANSS have been verified (SI Tianmei et al. , 2004) and applied in clinical practice. The internal consistency reliability was 0.87(Cronbach α). The internal consistency reliability of the 5 dimensions ranged from 0.74 ~ 0.90. The structure, validity and reliability of PANSS (Chinese version) are acceptable.

iii) Emotional assessment:

The emotional assessment was assessed by the Hamilton Depression Rating Scale (HAMD-17) and the Hamilton Anxiety Rating Scale (HAMA-14), which are among the most widely used scales for evaluating emotional status. HAMA-14 contains two aspects; physical and mental. It includes 14 items with a total score of 56. HAMD-17 covers; despair, somatization symptoms, sleep disorders, and anxiety. It consists of 17 items with a total score of 52. (Maier, 1988; Maier, 1990). The 2025 Expert Consensus on Neuropsychological Assessment of Mild Cognitive Impairment (2025) recommends the use of these scales, as they effectively identify and quantify depressive and anxiety symptoms in patients with MCI. These tools have been widely adopted due to their high sensitivity and specificity, as well as their ease of administration and interpretation.

11) Data analysis

Objective No. 1 and 2 : To develop and validate the psychomotor rehabilitation nursing plan through content/face validation using the Delphi Method for older adults with mild cognitive impairment in promoting cognitive health.

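### Section 11 uses the seven background variables only descriptively and specifies no covariate-adjusted between-group estimate, although group equals institution

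*Combined protocol and SAP*

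**What the plan says.** All references are to the Methodology part of the combined protocol and SAP.

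- **Design and allocation.** Item 1 describes a "Quasi-Experimental Design (Non-randomized controlled trial) with experiment and control groups for comparison". Under Phase 2 of item 9, treatment follows the site: "So the experimental group is JRH, and the control group is JPCSC". Item 5 defines the controls as "Older adults with MCI from Jinzhou Pension Comprehensive Service Center (JPCSC), without psychomotor rehabilitation nursing plan".
- **Sampling.** "8) Sampling method: Purposive sampling". No matching or stratification is stated.
- **Background data.** Phase 2 of item 10 records "age, gender, education level, family history of dementia, marital status, personal annual income, chronic disease". The Data Collection Form in the appendices carries all seven, with education in four categories.
- **Use of those data.** Item 11, Objective No. 3: "Descriptive statistics will be used to summarize the general information of older adults". Nothing further is planned for them.
- **Outcome analysis.** Item 11 and the summary name the paired t-test for every scale. The dummy tables are titled as comparisons of the two groups, but their columns are before and after, each with n = 76, and a difference. The Delphi experts have a dummy table of characteristics; the participants have none.
- **Education and MoCA.** The questionnaire section gives Beijing-version cut-offs for MCI of 13 or below for illiterate people, then "≤ 19 for those with primary education, and ≤ 24 for those with middle school education or higher". The appended MoCA form adds a point for 12 or fewer years of education.

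**The concern.** When site decides treatment, nothing makes the groups alike at baseline, so the analysis has to deal with differences between them. This plan collects the means to do so and does not use them. It also documents that its main cognitive measure depends on schooling. Entry is by Mini-Cog score, and no entry criterion balances education between the sites.

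Two things are at stake. First, a paired test on everyone together measures change in the pooled sample. It does not estimate the effect of the nursing plan against control. Second, the natural repair, an independent t-test between sites, would leave measured case-mix uncontrolled. Age or education could affect 12-week change through practice on a repeated test, ceiling effects or regression to the mean. If the sites differ on these variables, that part would be read as an effect of the plan.

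**Working it through.** **1. The plan's own figure.** Item 7 gives S = 2.75 and δ = 2.14 (both stated to be MMSE values), with 1.96 and 1.28 for α = 0.05 two-sided and β = 0.10. Then 2 × [(1.96 + 1.28) × 2.75 / 2.14]² = 34.67. The plan states 34 per group; 34 × 1.10 = 37.4, rounded up to 38, gives 76 in total. The figure reproduces to within rounding. It is a calculation for two independent means, so a between-group contrast was intended.

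**2. What section 11 delivers.** Set beside that calculation, the named test is paired and the tables hold 76 before and 76 after. No between-group test, regression, ANCOVA, matching, weighting or baseline comparison by group appears in the text.

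**3. How large the uncontrolled part could be.** The documents give no figure for how gain varies with education, so this is an assumption shown over a range. Consider a comparison of 12-week changes with 38 per group, within-category SD 2.75 and no true effect. Take three education categories (a simplification; the form has four), with equal thirds in the control group. A share s of the other group is moved from the lowest to the highest category, and g is the extra gain per category.

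- Bias b = 2 × s × g.
- SE = √[(2 × 2.75² + v₀ + v₁)/38], where v₀ = 0.667g² is the control group's between-category variance. For the other group v₁ = 0.507g² (s = 0.20) or 0.307g² (s = 0.30).
- False-positive rate = Φ(−1.96 + b/SE) + Φ(−1.96 − b/SE).

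| g (points) | s | b (points) | SE | False-positive rate |
|---|---|---|---|---|
| 0.25 | 0.20 | 0.10 | 0.632 | 5.3% |
| 0.25 | 0.30 | 0.15 | 0.632 | 5.6% |
| 0.5 | 0.20 | 0.20 | 0.637 | 6.1% |
| 0.5 | 0.30 | 0.30 | 0.636 | 7.6% |
| 1 | 0.20 | 0.40 | 0.655 | 9.4% |
| 1 | 0.30 | 0.60 | 0.651 | 15.2% |

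Simulation of the same set-up agrees. With education in the model, the bias disappears and the rate returns to about 5%.

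**4. Price in precision.** In the simulation at g = 1, adjusting for education alone raised the SE from 0.65 to 0.66 at s = 0.20, and from 0.65 to 0.70 at s = 0.30.

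For the full model, let ρ be the multiple correlation of baseline and covariates with the 12-week score, and R² the share of group membership that they explain (both assumed). The effective SD is 2.75 × √[(1 − ρ²)/(1 − R²)]. Power for δ = 2.14 with 34 evaluable per group is:

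| ρ | R² = 0 | R² = 0.1 | R² = 0.3 |
|---|---|---|---|
| 0.3 | 92% | 89% | 80% |
| 0.5 | 96% | 94% | 87% |
| 0.7 | 99% | 99% | 96% |

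The unadjusted comparison has 89.4%.

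**5. Degrees of freedom.** Baseline score 1, age 1, sex 1, education 3, chronic disease 1: seven in all. With 68 evaluable participants, 68 − 2 − 7 = 59 remain for error.

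**The case against.** The strongest reply is that the only named test is paired and pooled. It yields no contrast between institutions for case-mix to enter, and stable differences in level cancel within a person. The basic defect is then the missing between-group analysis, and covariates are a detail of its repair. The first part stands: a reader might infer that case-mix passes straight into the plan's effect estimate, and the documents do not support that, because they contain no such estimate. But a between-group comparison is plainly intended, and replacing the paired test with an independent one would not settle adjustment. The model has to be named when the contrast is added.

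A reader might also infer that education moves MoCA by 24 − 13 = 11 points. On that reading, a 10 or 20 percentage-point imbalance would shift the result by 1.1 or 2.2 points, or 51% or 103% of 2.14. The documents do not support this. The three values are diagnostic cut-offs from a cited community study of people aged 65 and over, not mean scores in participants enrolled from age 50 by Mini-Cog. They belong to the Beijing version, whereas the appended form is the original version 7.1. The 2.14 is an MMSE difference. A comparison of changes would also cancel a stable gap in level.

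Three further limits stand. Nothing in the documents shows that these two sites do differ in age or education. The gain per category is an assumption, and at 0.25 to 0.5 points the error rate barely moves. Adjustment is not free: if the sites differ strongly on the covariates, the interval can widen. That adjustment cannot remove site effects is also true, but it is no reason to leave the measured differences uncontrolled.

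**Conclusion.** The point holds in a limited form. In a non-randomised, purposively sampled comparison with one institution per group, section 11 specifies neither a between-group estimate nor any use of the seven background variables beyond description. An unadjusted two-group test would leave measured case-mix uncontrolled. The education-specific cut-offs and the education point on the form are good grounds to expect that education matters for MoCA, but they do not give its size.

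The size is hypothetical. Bias is about 0.1 to 0.6 points and the false-positive rate about 5 to 15%, against about 5% adjusted. This rests on an assumed differential gain of 0.25 to 1 point per category, an imbalance of 20 to 30 percentage points, three education categories, and an MMSE standard deviation used for MoCA change. The upper end needs both the largest gain and the largest imbalance.

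The change should be made because it is cheap and because following the present text would give a worse answer. No figure here shows that the result will be wrong. Even the adjusted estimate cannot separate the nursing plan from the institution that delivers it.

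**What to change.** In section 11, Objective No. 3:

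- Define the effect as the EG–CG difference in 12-week MoCA from a linear regression on group, baseline MoCA, age, sex, education category (the four on the form) and chronic disease (yes/no). Report it with its 95% CI, and the unadjusted difference beside it.
- Use the same model for PANSS, HAMA-14 and HAMD-17, each with its own baseline score.
- Add a participant baseline table by group with standardised differences.
- State as a limitation that site effects, such as usual care and staff, remain fully confounded with treatment whatever is adjusted for.

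Fixing the covariates now also prevents their being chosen after the data are seen. If family history, marital status and income stay out of the model, a sentence should say why.

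The cost is wording, one table and a little analysis; every variable is already on the form. The model spends about seven degrees of freedom. The interval may widen if the sites differ strongly on the covariates, although baseline MoCA may offset this. On the assumptions shown, power at 34 evaluable per group is 80 to 99%, and at least 87% once ρ reaches 0.5.
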